8.6.2. Additional Safety Assessments

Electrocardiograms

Summary will be provided for patient who experienced QTcF >500 msec on at least 2 of 3 electrocardiograms (ECG) and had the triplicate average QTcF greater than 500 msec.

Abnormal changes (also known as delta changes) of QTcF >60 msec will also be summarized. The changes will be derived as from maximum baseline QTcF interval to maximum QTcF interval during treatment.

Vital Signs

Treatment-emergent abnormal changes in vital signs will be summarized using descriptive statistics.

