| Adolescent Dose ^a | 92 mg/m ² BID | 40 mg/m ² QD | See dosing guide |
| Approximate Adult Equivalent dose | 160 mg BID | 72 mg QD | |
| Cycle length is 28 days for all treatment arms. | | | |

Abbreviations: BID = twice daily; QD = once daily

^a refer to respective nomograms in Section 6.1 for the exact dosing in adolescent patients. A reduced starting dose of vandetanib should be used in adolescent patients with moderate renal impairment as per the dose reduction table in Section 6.6.

[figure not shown]
^b starting dose of vandetanib should be 200 mg in adult patients with moderate renal impairment (creatinine clearance results between 30 and 50 mL/min). In case vandetanib 100-mg tablets are not available, see Section 6.6.

Ethical Considerations of Benefit/Risk:

Based on the manageable toxicity profile and evidence of durable antitumor activity in patients with advanced *RET*-mutant MTC, selpercatinib may be of benefit in delaying treatment failure and disease progression and in improving survival in patients with progressive, advanced MTC who have not previously received cabozantinib or vandetanib. Therefore, the sponsor considers that the benefit/risk balance is positive and supports the proposed Phase 3 Study JZJB, exploring administration of selpercatinib in comparison to cabozantinib or vandetanib in adult and adolescent patients.

Data Monitoring Committee: Yes

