|--|------------------------|----|-----------------|----|-----------|---------------------------------------|----------|-----------------------------------|----------------------------------|------|---|
| | Screening | | On-Treatment | | | Safety assessments prior to crossover | | Post-Study Treatment | | | Instructions |
| | | | Cycle = 28 days | | | (only for patients on Arm B) | | | | | |
| | (Day Relative to C1D1) | | Cycle 1 | | Cycle 2-n | V201 ^a | | Short-term follow-up ^a | Long term Follow-up ^b | | |
| | | | (±3 days) | | (±3 days) | Day 1-30 (±7 days) | 1-x days | (30 ± 7 days) | (90 ± 14 days) | | |
| ≤42 | | ≤7 | | D1 | D8 | D15 | D1 | N/A | N/A | V801 | V802-8XX |
| Procedure | | | | | | | | | | | |
| | | | | | | | | | | | followed every 30 days until the event is resolved, the event is no longer considered to be drug related, the event becomes stable or returns to baseline, a new treatment is initiated for the patient, or the patient dies or is lost to follow-up. |
| ECOG PS (≥18 years of age) | X | | X | | | See Instructions | X | | X | | During study treatment, perform ≤3 days prior to treatment, perform on Day 1 of Cycles 2-16, then obtain every 12 weeks in adult patients (Cycles 16, 19, 22, etc.). |
| ECOG PS (<18 years of age) | X | | X | | | X | X | | X | | During study treatment, perform ≤3 days prior to treatment. ECOG PS will be performed on adolescent patients every 4 weeks starting on Day 1 of Cycle 2-n and throughout. |
| ECG | X | | X | X | | See instructions | | | | | Obtain triplicate local ECGs at Screening, C1D1, C1D8, and on Day 1 of C2-6. It is preferable to obtain ECGs approximately 2 hours after dosing. Patients receiving vandetanib (Arm B2) continue to have ECGs performed every 3 months post Cycle 6 (consider additional ECG at C16D1 so subsequent ECGs align with onsite clinical visit schedule). See Section 8.2.1. |

| Screening, On-Study, and Post-Study Treatment Follow-Up Schedule of Activities for Patients on Arm A and Arm B | | | | | | | | | | | | |
|--|------------------------|----|-----------------|----|-----------|---------------------------------------|----------|-----------------------------------|----------------------------------|----------|--------------|--|
| | Screening | | On-Treatment | | | Safety assessments prior to crossover | | Post-Study Treatment | | | Instructions | |
| | | | Cycle = 28 days | | | (only for patients on Arm B) | | | | | | |

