 - In the ZETA study, the median PFS was 30.5 months for vandetanib-treated patients with newly diagnosed advanced MTC and patients with progression (Wells et al. 2012). A post hoc analysis provided median PFS results for two subgroups of patients that are similar to those enrolling in Study JZJB based on the presence of progressive disease within 12 months of enrollment. For those with both disease progression and symptoms in the prior 12 months, the median PFS was 21.4 months and for those with disease progression only in the prior 12 months, median PFS was not reached at a median follow-up of 95 months (Kreissl et al. 2020).

An initial assumption of 74 PFS events provides approximately 80% power to detect a hazard ratio (HR) of 0.5 using the logrank test and a 1-sided type I error of 2.5%. Given the historical data outlined above, a median PFS of 25 months is assumed for Arm B. HR of 0.5 corresponds to an improvement in median PFS from 25 months for Arm B to 50 months for Arm A. Approximately 250 patients will be enrolled based on these initial assumptions.

The sample size re-estimation will be based on PFS, so the sample size adjustment has the purpose of modifying the number of events. The number of patients will be adjusted to ensure the achievement of the required total number of events in an expeditious manner.

A re-estimation of the number of PFS events will be conducted only once, during the pre-specified interim efficacy analysis, based on the unblinded comparative results observed at this analysis. Based on prespecified criteria described in the Adaptive Design Charter the following scenarios are possible:

- the study will be declared positive due to overwhelming efficacy
- the study will continue without change to the final analysis (ie, the re-estimated total number of events will be equal to the initial planned total number of events)
- the re-estimated total number of events required for the final analysis will be determined and the study will continue to the final analysis.

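### The between-arm QTcF outlier summaries use all on-treatment ECGs, but after Cycle 6 only vandetanib patients have scheduled ECGs, so the pooled control arm can show more outliers through the schedule alone

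*SAP*

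**What the plan says.** The ECG row of the main schedule (Protocol 1.3.2) reads: "Obtain triplicate local ECGs at Screening, C1D1, C1D8, and on Day 1 of C2-6". After that the arms part: "Patients receiving vandetanib (Arm B2) continue to have ECGs performed every 3 months post Cycle 6". Neither selpercatinib nor cabozantinib has a scheduled ECG after C6D1. Protocol Section 8 allows extra ECGs in any arm at the investigator's discretion.

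SAP 8.6.2 plans two QTcF summaries. One counts patients above 500 msec on at least two of three ECGs whose triplicate average is also above 500 msec. The other is described as follows: "Abnormal changes (also known as delta changes) of QTcF >60 msec will also be summarized". Its derivation is: "The changes will be derived as from maximum baseline QTcF interval to maximum QTcF interval during treatment". Neither has a common window, an adjustment for the number of ECGs, or a split of Arm B by drug, although SAP 8.6.1 does split exposure by drug. SAP 8.1 limits analyses to the period before crossover unless stated otherwise, so ECGs taken on crossover selpercatinib do not offset the difference. Protocol 9.4.4 has other safety parameters summarized by treatment group where appropriate.

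**The concern.** The expected maximum of repeated readings rises with the number of readings, and so does the chance of ever meeting a threshold rule. Two groups with the same QT effect but different numbers of ECGs will show different proportions of outliers. Here the extra scheduled ECGs all fall in Arm B, among its vandetanib patients.

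Comparing safety between the arms is a secondary objective (Protocol Section 3). QT prolongation matters for selpercatinib itself: Protocol 2.2.1 reports it at Grade 3 or higher in 2.8% of patients in the earlier study. A table covering the whole treatment period could not separate drug effect from schedule. It would also suggest full coverage of selpercatinib treatment. Measured against the 50-month planning median for Arm A, scheduled ECGs cover about the first 4.6/50 = 9%.

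**Working it through.** The documents give no count of ECG occasions, so there is no stated figure to reproduce.

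**Inputs from the documents**
- On-treatment visits common to all arms: C1D1, C1D8 and Day 1 of Cycles 2 to 6, which is 7. C1D1 is counted because "It is preferable to obtain ECGs approximately 2 hours after dosing"; dropping it gives 6.
- Cycle length: "Cycle length is 28 days for all treatment arms". C6D1 is therefore day 5 × 28 + 1 = 141, and 141/30.4375 = 4.6 months.
- Planning medians (SAP Section 6): "HR of 0.5 corresponds to an improvement in median PFS from 25 months for Arm B to 50 months for Arm A". PFS is used here as a proxy for time on treatment.

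**Assumptions**
- Every 3 months is taken as 84 days.
- The vandetanib share of Arm B is not stated, so 25%, 50% and 75% are used.

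**Step 1: visits per patient at equal time on treatment**

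At 25 months (761 days), a vandetanib patient has (761 − 141)/84 = 7.4, so 7 extra visits and 14 in all.

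| Months on treatment | Vandetanib | Selpercatinib or cabozantinib | Ratio |
|---|---|---|---|
| 6 | 7 | 7 | 1.00 |
| 12 | 9 | 7 | 1.29 |
| 18 | 11 | 7 | 1.57 |
| 25 | 14 | 7 | 2.00 |
| 36 | 18 | 7 | 2.57 |

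**Step 2: pooled Arm B against Arm A at 25 months**

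With vandetanib share s, the ratio is [14s + 7(1 − s)]/7, which gives 1.25, 1.50 and 1.75 for s = 25%, 50% and 75%.

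**Step 3: expected visits with exponential time on treatment**
- Medians 25 and 50 months, 36 months' follow-up: vandetanib 12.9, cabozantinib 6.6, selpercatinib 6.8. Pooled Arm B has 1.20, 1.44 and 1.67 times the visits of Arm A.
- Full 72 months: 1.31, 1.66 and 2.00 times.
- An 11-month Arm B median with 24 months' follow-up: 1.01, 1.11 and 1.21 times.

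**Step 4: effect on the share with change above 60 msec**

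The simulation gives every drug the same effect. A patient's true shift has mean 10, 20 or 30 msec and between-patient SD 12. Between-visit SD is 10 and within-triplicate SD is 8. All these values are assumed. The change is the maximum on-treatment reading minus the maximum of one baseline triplicate, with 200,000 patients per cell.
- From 7 to 14 visits (a vandetanib patient at about 25 months), the share rises from 3.1% to 4.8%, 9.4% to 13.3% and 21.8% to 28.8% for the three mean shifts. The relative increases are 4.8/3.1 = 1.55, 13.3/9.4 = 1.41 and 28.8/21.8 = 1.32.
- Pooled Arm B against Arm A (exponential times, medians 25 and 50 months, 36 months' follow-up): at 20 msec the ratios are about 1.07, 1.16 and 1.25 for the three vandetanib shares. At 50% this is about 10.7% against 9.2%. Over all three shifts the range is about 1.05 to 1.34.
- The same model in the short-treatment case of Step 3 gives about 0.95 to 1.07, which is no material tilt.

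**Step 5: the common window**

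Restricted to scheduled ECGs through C6D1, every drug has 7 visits, a ratio of 1.0 for patients still on treatment.

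**The case against.** The strongest counter-argument is that these are descriptive tables. No test is planned on them and no endpoint or decision depends on them. QT prolongation is also reported through CTCAE-graded adverse events. That limits the weight of the point but does not make the planned table comparable between arms.

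A second argument is that the size rests on assumed SDs and mean shifts, on PFS as a stand-in for treatment time, and on a constant drug effect. This stands. Stopping early for toxicity shortens vandetanib exposure and lowers the ratio. Protocol 8.2.1 also requires vandetanib to be held and reduced once its QTcF criteria are met, although by then the patient would ordinarily already be counted.

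Third, the 500 msec rule needs a qualifying triplicate and is not a maximum of single readings. That is correct. It still accumulates over visits, but its inflation has not been calculated.

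Fourth, a table confined to the common window misses late and unscheduled events. This also stands, and is why the all-ECG summary must be kept.

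A reader might go further and infer that the control arm as a whole has twice the chance of showing an outlier. The documents do not support that. Cabozantinib patients follow the same ECG schedule as selpercatinib patients, the vandetanib share is not stated, and Protocol 6.1.3 allows control treatment to be limited to cabozantinib when vandetanib is unavailable. Twice the visits is also not twice the probability, because readings within a patient are correlated. Nor is this a finding about safety monitoring: it concerns how the collected ECGs are summarized.

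**Conclusion.** The point holds as a defect in a descriptive between-arm safety summary. Two facts can be checked directly: scheduled ECGs continue after C6D1 for vandetanib only, and SAP 8.6.2 neither sets a common window nor splits Arm B by drug. Nothing elsewhere in the two documents corrects this.

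The factor of 2 applies to scheduled visits for a vandetanib patient treated for about 25 months. For pooled Arm B the imbalance in visits is smaller and depends on the vandetanib share and on how long control treatment lasts. Under the planning medians, 36 months' follow-up and the assumed variances, the pooled share above 60 msec is inflated by roughly 5% to 35% relative, in selpercatinib's favor. If control treatment is short, the tilt largely disappears. Unscheduled ECGs, whose frequency is unknown, could change the net effect in either direction. It is worth correcting because the correction is cheap, but it does not bear on the primary endpoint.

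**What to change.** In SAP 8.6.2, base the between-arm comparison of both QTcF summaries (above 500 msec and change above 60 msec) on scheduled ECGs through C6D1. Show it for selpercatinib, cabozantinib and vandetanib separately, and for pooled Arm B.

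Keep the planned all-ECG summary in full, by drug, with the number of ECG visits per patient. Add a note that it is not comparable between arms because the ECG schedules differ after Cycle 6.

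The cost is a short addition to the SAP and one extra table, with no new ECGs and no change to patient management. The common-window table does not capture late or unscheduled events; these remain in the all-ECG summary, so nothing is lost from the report.

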8.7. Other Analyses

8.7.1. Demographic and Other Baseline Characteristics

Demographic and baseline patient and disease characteristics, historical diagnoses, preexisting conditions, and prior therapies will be reported for the ITT population using descriptive statistics.

8.7.2. Concomitant Therapy

A summary of preferred names of concomitant medication by treatment arm by decreasing frequency will be generated.

8.7.3. Poststudy Treatment Therapy

The numbers and percentages of patients receiving poststudy anticancer therapies will be provided by type of therapy (surgery, radiotherapy, or systemic therapy), by drug class and/or name, overall, and by line of therapy.

8.7.4. Follow-up Time

Follow-up time is defined as the time from the date of randomization until death from any cause or last date the patient is known to be alive and under follow-up. Follow-up time will be estimated using Kaplan-Meier estimation of potential follow-up (“reverse Kaplan-Meier”) (Schemper and Smith 1996). The inverse of the censoring rules for the OS will be used, ie considering all censoring times for OS as event times (times when the patient is known to be still alive and under follow-up) and censoring patients at the date of death.

Follow-up time will be compared across treatment arms using an unstratified logrank test and Kaplan-Meier estimates (Kaplan and Meier 1958).

8.7.5. Health Care Resource Utilization

Summaries of hospitalizations, emergency room visits, granulocyte-colony stimulating factor (G-CSF) use, transfusions, and analgesic use will be reported descriptively for each treatment arm. Due to potential differential treatment durations, hospitalizations and emergency room visits per on-treatment month will also be reported by arm.

Duration of hospital stays and average number of emergency room visits will be reported by treatment arm.

8.7.6. Pharmacokinetic/Pharmacodynamic Analyses

Selpercatinib plasma concentrations will be summarized by descriptive statistics. Additional analysis utilizing the population pharmacokinetics (PK) approach may also be conducted if deemed appropriate and described in a separate SAP. The relationship between selpercatinib plasma exposure and selected efficacy and safety outcomes may be explored.

8.7.7. Subgroup Analyses

To determine whether the treatment effect is consistent across various subgroups, the between-group treatment effect for OS, PFS, TFFS and ORR (with a nominal 95% CI) will be estimated and plotted within each category of the following subgroups (defined based on eCRF data):

- Age category (≤ 65 vs. > 65 years)
- Eastern Cooperative Oncology Group (ECOG) performance status (0 to 1 vs. 2)
- Sex (female vs. male)
- Race (Asian vs. non-Asian)
- Tissue vs. blood RET mutation detection
- RET mutation: M918T vs. other
- RET mutation: M918T vs. extracellular cysteine region (mutations in the exons 10 and 11) vs. other
- Investigator's choice of treatment with cabozantinib vs. vandetanib

If a level of a factor includes fewer than 5% of the ITT population, analysis within that level will be omitted. Additional subgroup analyses may be performed as deemed appropriate.

8.7.8. Analyses of Pandemic Mitigations

There may be times due to exceptional circumstances (eg, coronavirus disease 2019 [COVID-19] pandemic) where it may not be feasible for patients to come to investigator sites for study-required visits. To evaluate the impact of pandemic mitigations, missing visit/values will be summarized. Additional sensitivity analyses may be performed as deemed appropriate.

8.7.9. Clinical Trial Registry Analyses

Additional analyses will be performed for the purpose of fulfilling the Clinical Trial Registry (CTR) requirements. Analyses provided for the CTR requirements include the following:

- Summary of AEs, provided as a dataset which will be converted to an extensible markup language (XML) file. Both SAEs and "Other" AEs are summarized by treatment arms and by MedDRA PT.
- An AE is considered "Serious" whether or not it is a TEAE.
- An AE is considered in the "Other" category if it is both a TEAE and is not serious.
- For each SAE and "Other" AE, for each term and treatment arms, the following are provided:
 - the number of participants at risk of an event (if certain subjects cannot be at risk for some reason, for example, gender-specific AEs, then the number will be adjusted to only include the patients at risk)
 - the number of participants who experienced each event term
 - the number of events experienced.
- For each SAE, for each term and treatment arms, the following are also provided for the EudraCT results submission:
 - The number of occurrences (events) causally related to treatment
 - The total number of deaths
 - The number of deaths causally related to treatment

- Consistent with www.ClinicalTrials.gov requirements, a threshold for frequency of “Other” AEs can be implemented rather than presenting all “Other” AEs. For example, “Other” AEs that occur in fewer than 5% of patients in any treatment arms may not be included if a 5% threshold is chosen. The frequency threshold must be less than or equal to the allowed maximum of 5%.
- A participant flow will be created that will describe:
 - Number of participants per treatment arm. Screen failures do not need to be included. Number of participants who did not complete the study per treatment arm. This analysis will be based on study discontinuation, not treatment discontinuation.
 - Reasons participants did not complete the study.

8.8. Interim Analyses

An interim analysis will be triggered after approximately 56 PFS events by BICR have occurred (at 75% information fraction). Based on the observed HR of PFS by BICR and pre-specified criteria, the study results at interim analysis will be categorized into 4 determination zones: efficacious, favorable, promising, and unfavorable.

- If the study results fall into the **efficacious** zone, a positive study will be declared due to overwhelming efficacy, enrollment will be stopped, and regulatory interactions will be initiated.
- If the study results fall into the **favorable** zone, the study will continue to the final analysis with the initially planned total number of events at 74 (ie, no re-estimation will be conducted).
- If the study falls into the **promising** zone, the total number of events will be increased. The events re-estimation will be based on the observed PFS HR according to the method provided in Cui, Hung, and Wang (Cui et al. 1999). The total number of patients will be increased and determined accordingly so that the required number of events could be achieved in a desired timeframe.
- If the study results fall into the **unfavorable** zone, enrollment will be halted, and the study will continue to the final analysis.

The critical boundary of efficacious zone to declare a positive study is determined by the Rho family alpha spending function with $Rho=12$ (Kim and DeMets 1987), based on consideration of being more conservative than O’Brien Fleming alpha spending function in stopping at the interim analysis. The one-sided alpha spent at the interim analysis is 0.00088. The p-value, Z scale, and HR critical boundaries are shown in [Table JZJB.11](#) for reference only and will be updated based on the actual number of events observed at the time of interim and final analysis.

[figure not shown]
The decision boundary of other zones and the algorithm of sample size re-estimation will be described in the Adaptive Design Charter.

Table JZJB.11. Efficacy Analyses

Efficacy Analysis	Information Fraction	Number of PFS Events by BICR to Trigger Analyses	1-sided P-value Critical Boundary	Z Scale Critical Boundary	HR Critical Boundary
Interim	75%	56	0.00088	-3.127	0.412
Final	100%	74 – 284	0.02497	-1.960	TBD

Abbreviations: BICR = Blinded Independent Central Review; HR = Hazard Ratio; PFS = Progression-Free Survival; TBD = To Be Determined.

The figure below provides an overview of the proposed adaptive design. Sample size/total number of events determination will be conducted at the interim efficacy analysis. If the study is not declared positive, final analysis will be conducted according to a determination zone (favorable, promising, or unfavorable) where the interim results fall. At final analysis, the study will be declared positive if the critical boundary is met.

Abbreviations: IF=Information Fraction; HR=Hazard Ratio

Figure JZJB.1 Overview of Proposed Adaptive Design

Conditional on PFS by BICR achieving statistical significance, TFFS by BICR will be tested and then comparative tolerability. Both TFFS and comparative tolerability will be formally tested at most once at final analysis. A nominal alpha of 0.00001 will be spent for interim analysis and both key secondary endpoints will be tested against 1-sided significance level of 0.02499 at final analysis.

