9.4.3.2. Key Secondary Analyses

9.4.3.2.1. Treatment Failure Free Survival

Treatment Failure Free Survival (TFFS) per BICR is defined as the time from randomization to the first occurrence of:

- documented radiographic disease progression per RECIST 1.1 as assessed by BICR; or
- unacceptable toxicity leading to treatment discontinuation as assessed by the investigator. To qualify as an event, the toxicity must be from an intolerable AE (defined as any study drug-related AE that meets protocol guidance for treatment discontinuation, with the exception of alopecia); or
- death (due to any cause).

An independent review committee will review blinded data to determine whether an AE leading to treatment discontinuation meets protocol guidance and thus should be considered as a TFFS event. Independent review will occur retrospectively and will not impact patient care decisions or study conduct.

Since TFFS events include PFS events with additional events of treatment failure due to toxicity, TFFS is sufficiently powered as result of sample size determination based on PFS events. TFFS will be analyzed at the time of the final analysis which is triggered by the PFS events.

Conditional on achieving a statistical significance for the primary endpoint of PFS, TFFS will be tested in a manner that will preserve the 1-sided overall type I error rate at 2.5%:

- If the study remains at the initial planned total number of PFS events and sample size, the TFFS will be compared between treatment arms using a stratified logrank test, stratified by the 2 randomization strata based on IWRS data: RET mutation (M918T vs. other) and intended control treatment (cabozantinib vs. vandetanib).
- If the total number of PFS events required for the final analysis increases after sample size re-estimation, the TFFS will be compared between treatment arms using the CHW test in a similar manner of the primary efficacy analysis. Details will be described in the SAP.

The corresponding HR between treatment arms will be estimated using a stratified Cox regression model (Cox 1972), stratified by randomization strata. Treatment failure free survival curves, medians, and TFFS rates at various time points with 95% CI for each treatment arm will be estimated using the Kaplan-Meier method (Kaplan and Meier 1958).

TFFS censoring scheme and sensitivity analyses will be described in the SAP.

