8.4.1.1.3. Main Analytical Approach

Since TFFS events include PFS events with additional events of treatment failure due to toxicity, TFFS is sufficiently powered as result of sample size determination based on PFS events.

Conditional on achieving a statistical significance for the primary endpoint of PFS, TFFS by BICR will be tested once at the time of the final analysis which is triggered by the PFS events, in a manner that will preserve the overall Type I error rate at the 1-sided significance level of 0.025 (see Section 8.8 Interim Analyses for details).

- If the study remains at the initial planned total number of PFS events and sample size, the TFFS will be compared between treatment arms using a stratified logrank test, stratified by the 2 randomization strata based on IWRS data: RET mutation (M918T vs. other) and intended control treatment (cabozantinib vs. vandetanib).
- If the total number of PFS events required for the final analysis increases after sample size re-estimation, the TFFS will be compared between treatment arms using the CHW test in a similar manner of the primary efficacy analysis:

Table JZJB.6. Defining the Values for Computing the CHW Test Statistic of TFFS

Quantity	Input Value or Derivation / Calculation
$Z_{TFFS,1}$	This is the stratified logrank test statistic comparing TFFS between treatment arms at the interim analysis. The interim analysis is triggered after approximately 56 PFS events have occurred (at 75% PFS information fraction).
$Z_{TFFS,2}$	This is the stratified logrank test statistic comparing TFFS between treatment arms at the final analysis.
$e_{TFFS,1}$	This is the observed number of TFFS events across both treatment arms at the interim analysis.
$e_{TFFS,2}$	This is the number of TFFS events across both treatment arms at the final analysis should the study remain at the initial planned 74 total number of PFS events. This number is projected to be 88 assuming a median TFFS of 20 months for Arm B (Wells et al. 2012) and HR of 0.5. $e_{TFFS,2} = 88$
$e_{TFFS,2}^*$	This is the observed number of TFFS events across both treatment arms at the final analysis.

Given the quantities defined in Table JZJB.6, the final CHW test statistic for the TFFS analysis can be written as:

$$Z_{TFFS,CHW} = \sqrt{\frac{e_{TFFS,1}}{e_{TFFS,2}}} Z_{TFFS,1} + \sqrt{\frac{e_{TFFS,2} - e_{TFFS,1}}{e_{TFFS,2}}} \left\{ \frac{\sqrt{e_{TFFS,2}^*} Z_{TFFS,2} - \sqrt{e_{TFFS,1}} Z_{TFFS,1}}{\sqrt{e_{TFFS,2}^* - e_{TFFS,1}}} \right\}$$

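### If PFS succeeds at the interim, does the plan leave the TFFS and comparative tolerability tests without a time or a data cutoff?

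*SAP*

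**What the plan says.** SAP Section 8.8 sets the timing for both endpoints in one sentence, "Both TFFS and comparative tolerability will be formally tested at most once at final analysis", and gives the level: "both key secondary endpoints will be tested against 1-sided significance level of 0.02499 at final analysis". A nominal 0.00001 is assigned to the interim. SAP Section 8.4.1.1.3 repeats the timing for TFFS ("TFFS by BICR will be tested once at the time of the final analysis which is triggered by the PFS events"), as does protocol Section 9.4.3.2.1 ("TFFS will be analyzed at the time of the final analysis which is triggered by the PFS events"). None of these sentences depends on the look at which PFS succeeds.

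The branching text is less complete. For the efficacious zone, SAP Section 8.8 says that "a positive study will be declared due to overwhelming efficacy, enrollment will be stopped, and regulatory interactions will be initiated". It then introduces the final analysis conditionally: "If the study is not declared positive, final analysis will be conducted according to a determination zone", naming the other three zones. Protocol Section 9.5 does the same. The list of interim outcomes in SAP Section 6 has the same shape: under the first, "the study will be declared positive due to overwhelming efficacy", while under the second, "the study will continue without change to the final analysis", and the third also continues.

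SAP Section 7 admits to the Tolerability Evaluable Population patients first dosed before the interim and at least six months before a data cutoff. It does not say which cutoff.

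**The concern.** TFFS and comparative tolerability are the only secondary claims under type I error control. Read literally, the plan ties them to a final analysis and then describes that analysis only for trials that did not succeed early. On the best outcome for the sponsor, the two tests would either have no stated occasion, or have a look and cutoff fixed after the PFS result is known.

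The choice would matter. An interim cutoff gives fewer TFFS events, and the six-month rule then removes more patients from the tolerability set. Testing at whichever look PFS happens to succeed, at the full 0.02499, would also let TFFS type I error drift above 0.025.

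**Working it through.** **1. Reproduce the plan's boundaries.** Inputs from SAP Sections 4.2, 6 and 8.8: interim at 56 of 74 PFS events, Rho = 12, one-sided 0.025, 2:1 allocation.
- Interim alpha: 0.025 × (56/74)^12 = 0.00088, so Z = 3.127.
- HR boundary: exp(−3.127 / √(56 × 2/9)) = exp(−3.127 / 3.528) = 0.412.
- Final boundary from the bivariate normal: p = 0.02497, Z = 1.960.

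All agree with Table JZJB.11. For the key secondaries, 0.00001 + 0.02499 = 0.025.

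**2. How often the branch is reached.** P = Φ(√(56 × 2/9) × (−ln HR) − 3.127).
- HR 0.5: Φ(2.445 − 3.127) = 0.248.
- HR 0.45: 0.378.
- HR 0.4: 0.542.

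The branch is not remote.

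**3. What the text implies there.**
- *Look:* the final analysis, because the interim carries only 0.00001.
- *Event count:* 74 is the planned total in SAP Section 6 and the lower end of the final trigger in Table JZJB.11. Only the promising zone increases it.
- *Follow-up:* the efficacious zone stops enrollment. Protocol Section 9.4.3.2.3 and SAP Section 8.4.2 continue the study to about 125 deaths or six years. Protocol Section 8.1.1 continues imaging until progression confirmed by central review, or death. Protocol Section 8.9.1 continues weekly questionnaires for as long as treatment lasts.
- *A final analysis is presupposed:* protocol Section 6.7.1 defines study completion by a final analysis of primary and secondary endpoints, and SAP Section 8.8.1.1 ties sponsor access to aggregate data to the final-analysis lock.

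**4. Properties of that default for TFFS.** A false TFFS claim requires the TFFS statistic at the fixed look to cross its boundary. That has probability 0.02499 whatever PFS does, and the PFS gate can only lower it. Simulation (4 million draws, PFS HR 0.4 to 0.7, PFS–TFFS correlation 0.85 or 0.90 assumed) gives 0.0249 to 0.0251.

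With exponential times, control medians of 25 months (PFS) and 20 months (TFFS), HR 0.5, 250 patients and uniform accrual over an assumed 18 to 36 months, about 67 TFFS events are expected at 56 PFS events and 87 to 88 at 74. The SAP projects 88. Power for a TFFS HR of 0.5 is Φ(√(events × 2/9) × 0.693 − z):

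| Look | TFFS events | One-sided alpha | Power |
|---|---|---|---|
| Interim | 67 | 0.00001 | 5.6% |
| Interim | 67 | 0.02499 | 76.3% |
| 74 PFS events | 88 | 0.02499 | 86.5% |

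**5. The tolerability set.** Membership closes at the interim whichever cutoff applies. The interval from 56 to 74 events is 5.5 to 6.3 months. It is 6.2 to 6.6 months if 36-month accrual is cut short at the interim. Patients qualifying, under the same accrual assumptions and PFS HR 0.5:

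| Accrual (months) | Enrolled by interim | Qualify, cutoff at 74 events | Qualify, cutoff at interim |
|---|---|---|---|
| 18 | 250 | 250 | 239 |
| 24 | 250 | 250 | 213 |
| 30 | 247 | 243–244 | 197 |
| 36, stopped at interim | 228 | 228 | 186 |

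At HR 0.4 the 74-event cutoff loses nobody enrolled by the interim. The large losses arise only with an interim cutoff, which the text does not assign to this test.

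**6. The type I error drift.** With one test at 0.02499 at whichever look PFS succeeds, TFFS type I error is 0.0264 / 0.0260 at PFS HR 0.5 (correlation 0.85 / 0.90) and 0.0252 / 0.0249 at HR 0.4. It peaks at 0.0292 / 0.0300 near HR 0.65. Over correlations from 0.5 to 1.0 the maximum runs from 0.026 to 0.034. This describes a rule the SAP does not contain.

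**The case for a change.** The strongest reply is that a confirmatory rule should be written down, not inferred. The conditional sentence in SAP Section 8.8 does leave the efficacious zone out. Follow-up running to about 125 deaths or six years means a cutoff later than 74 PFS events is also physically available. The SAP cites the Adaptive Design Charter for zone boundaries and re-estimation, not for the timing of secondary tests. The overview figure (Figure JZJB.1) could not be seen, so neither source can be assumed to fill the gap.

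This stands as a criticism of drafting: no passage restates the event count or cutoff for this branch. It does not show an open choice of look, because the alpha split and the at-most-once rule exclude a test at the interim at 0.02499, and no zone other than promising moves the target from 74.

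A second argument is that spelling out the wait to 74 events costs nothing. It would add about six months of open-label follow-up after a positive result is known, during which FACT-GP5 answers and investigator decisions to stop for toxicity could be affected. Reading out at the interim would avoid that exposure but give fewer events. Reasonable statisticians differ on which is preferable.

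**Conclusion.** No change follows. The plan names the look, the level and the single test. What it omits is a restatement, for one interim outcome, of the count of 74 that it uses everywhere except the promising zone. Filled in that way, type I error is 0.025, TFFS power is about 86% at a TFFS HR of 0.5, and the six-month rule removes at most about four patients enrolled by the interim.

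The type I error figures of 0.026 to 0.034 and the smaller tolerability sets belong to an interim-cutoff test that the text does not provide for. The timing and patient counts rest on exponential event times and an assumed accrual of 18 to 36 months. The simulated error rates rest on an assumed PFS–TFFS correlation. The bound of 0.02499 at a fixed look needs neither assumption.
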